	Outcome Measure	Visit 1 (admission visit)	Visit 2 (2 months)	Visit 3 (4 months or end of study)	Visit 4 (6 months or end of
--	-----------------	---------------------------------	-----------------------	--	-----------------------------------

					study)
Aim 1	Adherence (continually monitored during trial)		X	X	X
Aim 2	Communication among providers	X			X
Aim 3	Asthma Related Health outcomes	X	X	X	X

- a. Adherence- measured on adherence monitoring devices. The rate of daily prescribed controller medication use will be monitored. For example, if an individual is prescribed two doses per day and the monitoring device records one doses, then the daily adherence measure will be 1/2 or 50%. The outcome measure will be continuously gathered via the Propeller Health monitoring device ® (Madison, WI). Rate of monthly adherence will be calculated between study visits,
- b. Communication between providers. Communication between providers will be measured in a number of ways. Providers include nurses, parents, physicians and patients. In order to measure any change in communication the following communication metrics will be monitored.
 - i. Number of emails sent between providers will be assessed if email is used as the primary means of communication.
 - ii. A subset of provider teams will possibly be enrolled in asynchronous communication monitoring. This is a method of HIPAA compliant messaging, which involves providers utilizing an application or website, and communicating securely within that platform. We plan to utilize the Stich platform, which is marketed as HIPAA compliant (<https://www.teamstitch.com>). We are currently on a waiting list to possibly test the technology.
 - iii. Providers will be surveyed before and after the intervention to determine if they felt that the navigators adequately improved communication regarding specific patient related issues.
- c. Other asthma related outcomes including asthma control test, symptom assessments, asthma related readmissions or revisits, missed school days, and provider satisfaction.
 - i. Asthma Control Test, a self (or in the case of this study, phone administered)-administered questionnaire with 5 questions which summarizes asthma control, will be used to record asthma control in children 12 or older.
 - ii. Childhood Asthma Control Test (or in the case of this study, phone administered), a parent and child administered questionnaire, will be used to record asthma control for children 6-11 years of age.

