Demographic information including age, sex, race, and other baseline clinical information upon recruitment including duration of asthma, C-ACT score, ACT score, asthma symptoms, lung function, prescribed medication, and asthma related health care use in the previous year will be obtained at enrollment. The distributions of outcomes will be examined for normality using the Anderson-Darling Test. Dependent upon the distribution we will use the Wilcoxon rank-sum test, Mann-Whitney U test or paired T-test to test for significant changes in outcomes during the study period. Longitudinal patterns of adherence will be examined graphically.

Monthly rates of adherence, asthma symptoms, asthma control scores and monthly missed number of school days and number of hospitalizations will be calculated by study arm. Survey information from patients, caregivers, physicians and navigators on the navigator intervention will be reviewed by study staff and summarized qualitatively. Number of rehospitalizations will be obtained via chart review at 1 month, 6 months and 12 months post hospitalization.

The cost-effectiveness of the navigator intervention will be summarized based on medical resource utilization (direct) and loss of productivity (indirect). Medical resources utilization will include medical care resource utilization, asthma medication variables, navigator time and salary, while loss of productivity will be measured using the number of hours caretaker missed work due to participant's asthma, number of hours dependent participant missed school due to his/her asthma, and number of hours independent participant missed work due to his/her asthma. Unit costs will be applied to healthcare resources and loss of productivity and summed to obtain total costs for each subject. Average costs for the study group will be presented.

Power and Sample Size

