The study is limited by time frame and funding for a one year recruitment period. The primary goal of the study is to provide preliminary information on the effect of a navigator program on the patient and caregiver response to asthma disease control. As a pilot and feasibility study, investigators have chosen to enroll a total of 100 patients and up to 400 providers. Through past clinical experience, we know that some months of the year are higher risk for asthma exacerbations, so we expect to screen more patients during the fall and winter than summer or spring. Considering the variable clinical case load Investigators plan on enrolling an average of 10 participants per month. Anticipating an enrollment rate of approximately 20% (in 2015, there were >600 asthma related admissions at Children's Hospital Colorado), investigators state they should be able to enroll up to 100 patients within one year. We plan to enroll up to 4 providers per patient with a simple pre-post survey as well.

The primary hypothesis of interest is to test whether change in adherence rates are different from zero. The smallest detectable difference was based on a paired sample t-test between pre and post adherence scores with a Type I error rate of 0.05 and 90% power. Based on previous studies⁸, investigators assumed a mean adherence rate of 50% with a standard deviation of 22%.

Table X:	
N	Δ
100	8%
65	10%
30	15%

Table X lists the smallest detectable difference (Δ) for by sample size. For the primary aim investigators will be able to detect a change of 8% or more in percent adherence during the study period with the available 100 patients.

F. Summarize Knowledge to be Gained:

- a. **Utility of an asthma navigator in addition to electronic adherence monitoring in improving adherence to asthma medications**
- b. **Utility of an asthma navigator in improving communication amongst all of a patient's medical providers**
- c. **Utility of an asthma navigator in improving other asthma control related outcomes.**

Asthma Control Classification

Control is computed based on taking the entry with the worst outcome in the following age-based tables:

Asthma Control Classification (Age 5-10)

(Age 5-11)	Asthma	Control	Classification
	Well controlled	Not well controlled	Very poorly controlled
Symptoms (manually entered)	≤ 2 days/week but not more than once on each day	> 2 days/week or multiple times on ≤ 2 days/week	Every day in previous week

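### The test for change is chosen by a normality check on the outcome distributions, and the only non-normal option named ignores the pairing, so the analysis run may not be the paired t-test that was sized

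*Combined protocol and SAP*

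**What the plan says.** Section IV.F (Data Analysis Plan), under Analysis plan, sets a two-step rule. First: "The distributions of outcomes will be examined for normality using the Anderson-Darling Test". Then: "Dependent upon the distribution we will use the Wilcoxon rank-sum test, Mann-Whitney U test or paired T-test to test for significant changes in outcomes". It gives no significance level for the check. It does not say whether each time point or the within-child change is examined, or what follows if time points disagree.

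Section IV.A (Outcome Measures), item a, defines adherence as recorded over prescribed doses and adds: "Rate of monthly adherence will be calculated between study visits". The adherence outcome is therefore a level.

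Under Power and Sample Size, the primary hypothesis is to "test whether change in adherence rates are different from zero". The sizing attaches no condition to the test: "The smallest detectable difference was based on a paired sample t-test between pre and post adherence scores". Alpha is set at 0.05 and power at 90%. The assumed mean is 50% and the SD 22%. Table X gives a detectable change of 8% at N=100.

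**The concern.** A paired t-test uses one number per child, the change. Its validity depends on how the mean change behaves, and at N=100 that is usually close to normal. Adherence is bounded between 0 and 100%, so its distribution at a single time can be flat or skewed while the changes are well behaved. A check on levels can therefore reject normality when nothing is wrong with the paired t-test.

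The consequence depends on the fallback. Rank-sum and Mann-Whitney U are two names for one procedure that treats pre and post values as coming from different children. With positively correlated measurements it overstates the variance of the difference and loses power. At stake is whether the primary analysis is the one for which 90% power is claimed, and whether that is settled before the data are seen.

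**Working it through.** **Inputs from the protocol.** N=100, mean 50%, SD 22%, change of 8 points, alpha 0.05 (two-sided, since the hypothesis is a difference from zero), 90% power.

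**Assumptions, because the protocol is silent.** Beta-shaped adherence, a pre-post correlation ρ, a check at 5%, and two measurements per child.

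**1. The plan's own figure.** For a paired t-test, Δ ≈ (1.960 + 1.282) × SD of change / √N.
- With SD of change 22: 3.242 × 22 / 10 = 7.13, or 7.20 by the noncentral t. Table X says 8. At N=100 and Δ=8 these inputs give 95% power.
- With 22 as the SD of the level, SD of change = 22 × √(2(1−ρ)). Table X at 90% power needs about 24.5, which implies ρ ≈ 0.38.
- At ρ=0.5 the SD of change is 22 × √1 = 22.

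So ρ from 0.38 to 0.5 covers both ways of reading the 22%. Table X is under-documented on this, but the point here does not turn on it.

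**2. Cost of ignoring the pairing (normal approximation).** The unpaired standard error is 22 × √(2/100) = 3.11. The true standard error of the mean change is 3.11 × √(1−ρ), which is 2.45 at ρ=0.38 and 2.20 at ρ=0.5. An unpaired test rejects when the difference exceeds 1.96 × 3.11 = 6.10.

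| | ρ=0.38 | ρ=0.5 |
|---|---|---|
| Paired power, Φ(8/SE − 1.96) | Φ(1.31) = 90% | Φ(1.68) = 95% |
| Unpaired power, Φ((8 − 6.10)/SE) | Φ(0.78) = 78% | Φ(0.86) = 81% |
| Unpaired type I error, 2Φ(−6.10/SE) | 1.3% | 0.6% |

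**3. How often the check would divert the analysis (simulation, N=100, SD 22%).**
- No change, mean 50% at both times, ρ about 0.4: a single time point fails in 27% of trials, at least one of the two in 47%, and the changes in 5%.
- Means 50% to 58%, ρ 0.38 to 0.5: at least one time point fails in about 61-64%, the changes in about 4%.
- Pre and post give different verdicts in about 40-50% of trials.

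**4. Power for the 8-point change under each reading (same settings, ρ 0.38 to 0.5).**

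| Rule | Power |
|---|---|
| Paired t-test always | 89-96% |
| Rank-sum if either time point fails | 82-86% |
| Rank-sum only if both fail | 87-93% |
| Rank-sum if the changes fail | 88-95% |
| Signed-rank if either time point fails | about 0-2 points below always paired t |

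**5. Type I error.** With no change and ρ about 0.4, the unconditional paired t-test stays at about 5% in every N=100 scenario. Using rank-sum if either time point fails gives 3.1% at mean 50%. In a separate run at ρ=0.5, the same check with a signed-rank fallback gave 4.7-5.2%.

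**6. Sensitivity.** The background section cites adherence rates of 28-73%. At means of 28%, 65% and 73% with no change (SD 22%), at least one time point fails in 98-100% of trials and the changes in 8-26%. For 28% to 36% and 65% to 73%, power is about 90% with the paired t-test and about 86% under the either-fails rule. At N=30 with a pre mean of 50%, the either-fails rate drops to 14-17%.

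**The case against.** The strongest reply is that the harm comes from the fallback and not from checking normality. That is correct. Keeping the same check on the same levels but using the signed-rank test loses about 0-2 points of power and does not inflate type I error. A reader might infer that the rule would do material harm whichever non-parametric test was named; the calculations do not support that.

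Second, the text does not say that levels at each time point are tested, or that one failure is enough. Levels are the natural reading, because the plan words outcomes and changes in outcomes separately and defines adherence as a rate. A check on the changes is not excluded, and under that reading the loss is about one point. So it goes too far to say that the plan definitely tests the wrong variable. What stands is that the variable is unspecified and that the natural reading is the costly one.

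Third, the beta shape is assumed, and this is a single-group pilot that admits limited power for some outcomes. Both are fair. The pilot still states a primary hypothesis, an alpha, 90% power and a detectable change, and those figures need a fixed test. The rule makes the test conservative, so false-positive inflation is not part of this point.

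**Conclusion.** The point holds in a limited form. The plan lets a normality result choose between the paired t-test on which it was sized and a test that ignores pairing, so the analysis run may not be the one with the stated power. At the protocol's mean, SD and N, the loss is about 7 to 10 points if either failing time point triggers rank-sum (89 − 82 and 96 − 86). It is about 2 to 3 points if both must fail (89 − 87 and 96 − 93), and about 1 point if the changes are checked (89 − 88 and 96 − 95). These figures rest on the beta shape, a correlation of 0.38 to 0.5 and a 5% check, none of which the protocol states.

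A reader might go further and conclude that the primary analysis will probably not be the paired t-test. That does not follow. At the planning mean with no change, the diversion rate is 27% for one time point and 47% for either of two. It exceeds half only under the either-fails reading with a real rise, or with more skewed adherence. The change is worth making because it replaces a stated data-driven rule with the test the study was sized on, at almost no cost.

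**What to change.** In Section IV.F, under Analysis plan:

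- State that the primary adherence analysis is the paired t-test on within-child change, reported with a 95% CI, whatever the result of any normality check. This matches Power and Sample Size.
- Replace rank-sum and Mann-Whitney U with the Wilcoxon signed-rank test, as a fixed sensitivity analysis.
- If the Anderson-Darling check is kept, apply it to the within-child changes and use it descriptively, not to select the test.

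The cost is two or three sentences. Data collection and sample size do not change.

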At the time of enrollment, patients will be asked for permission to contact the child's primary care provider and school nurse. If these providers agree to participate in the study, surveys will be sent to all providers of patients (PCPs, school nurses and specialists) to determine if they found the navigator to be helpful, and to see if communication increased due to the intervention. Additionally, the research coordinator will be monitoring the provider portal to ensure that patients' devices are regularly syncing with their phone's Bluetooth, and contact any patients whose devices are not syncing normally. At the study's conclusion, we will plan to have the families return the devices to the research coordinator via US mail. After the conclusion of the study, families will be contacted by the research coordinator to ask if they would be willing to evaluate the navigator via the PSN-I navigator assessment tool. The navigator assessment tool will be used to evaluate utility of the navigator themselves. This is a tool that has been utilized previously in this context to evaluate efficacy of navigator programs. This will only be evaluated at the end of the study. There will be no reimbursement for time for this last survey.

If a patient is having difficulties with syncing their sensors to their phone, we will provide them with a hub to collect the sensor data.

D. Description, Risks and Justification of Procedures and Data Collection Tools:

There will be no medical procedures done during this study. The data collection will occur via surveys, and data collected from the adherence devices. Risks of data collection include accidental disclosure of information, though steps will be taken to prevent this. Also, there is a GPS capability of the devices, so there is a risk of disclosure of patient's location patterns.

E. Potential Scientific Problems:

We are aware that we are underpowered to fully evaluate some of the outcomes that we are interested in obtaining. Additionally, we are limited to single group analysis by request of the funding agency (rather than also having a control group), so we are limited in our ability to make full comparisons. However we would like to undertake this study as a pilot evaluation for the use of the asthma navigator in this population, utilizing adherence monitoring technology to better understand the influence of these evaluations.

F. Data Analysis Plan:

Analysis plan

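### The only rank test named for pre/post change is an independent-samples test, although the design is a paired single group

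*Combined protocol and SAP*

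**What the plan says.** Three places in the combined protocol and SAP bear on this point.

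- **Section IV.F, Analysis plan.** The test is chosen by distribution: "The distributions of outcomes will be examined for normality using the Anderson-Darling Test", and then "we will use the Wilcoxon rank-sum test, Mann-Whitney U test or paired T-test to test for significant changes in outcomes".
- **Section IV.E, Potential Scientific Problems.** There is no control group: "we are limited to single group analysis by request of the funding agency". The same section concedes low power for some outcomes.
- **Power and Sample Size.** "The primary hypothesis of interest is to test whether change in adherence rates are different from zero". The detectable difference comes from a "paired sample t-test between pre and post adherence scores", with type I error 0.05, 90% power, mean adherence 50% and SD 22%. Table X gives 8% at N=100, 10% at N=65 and 15% at N=30. For providers: "We plan to enroll up to 4 providers per patient with a simple pre-post survey as well".

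No signed-rank, sign or other paired rank test appears in the document.

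**The concern.** The parametric branch of the rule is paired and the non-parametric branch is not. An analyst who follows the text would, for a non-normal outcome, treat the pre and post values of the same children as two unrelated samples.

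The rank-sum test takes its standard error from independence. If a child's two values are positively correlated, that standard error is too large. The test then rejects too rarely under the null and misses real changes more often.

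The trigger for this branch is also misplaced. The paired t-test relies on the distribution of the within-subject differences, but the check is written for the outcomes themselves. Bounded percentages and skewed counts can fail that check even when their differences are close to normal. The affected outcomes are those measured repeatedly on the same patient: adherence, asthma control scores and missed school days. Provider surveys are affected only if pre and post responses are linked, which the document does not say.

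**Working it through.** **Inputs from the document.** N=100, change 8 points, SD 22, alpha 0.05 (read as two-sided, because the hypothesis is a difference from zero), 90% power, paired t-test.

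**Not in the document.** The pre/post correlation ρ, so a range is used.

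**1. Table X.** The normal approximation to the detectable change is (1.960 + 1.282) × SD of change / √N. With SD of change 22 and N=100 this is 3.242 × 22 / 10 = 7.13; the noncentral t gives 7.20. For N=65 and N=30 the noncentral t gives 8.98 and 13.47. The literal inputs therefore do not return 8, 10 and 15. Two readings do:

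- 90% power with SD of change 24.44, 24.50 and 24.49 for the three rows. If 22 is the SD at each time, ρ = 1 − SD_change² / (2 × 22²) = 1 − 24.5² / 968 = 0.38.
- 95% power with SD of change 22, which gives 8.01, 9.99 and 14.99.

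So 0.38 is one reading of the table and not a stated value. It serves below as one point in a range.

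**2. Type I error of rank-sum on paired normal data.** The test assumes var(P̂) = 1/(6n), where P̂ estimates P(post > pre) across all pairings. Under pairing the variance is about (1 − ρ_S)/(6n), with ρ_S = (6/π) arcsin(ρ/2). True size ≈ 2Φ(−1.960 / √(1 − ρ_S)). At ρ = 0.38, ρ_S = 0.365 and √(1 − 0.365) = 0.797, so the size is 2Φ(−2.46) = 1.4%.

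**3. Power of rank-sum.** The shift in P̂ is Φ(8 / (22√2)) − 0.5 = 0.1015. The assumed standard error is √(1/600) = 0.0408, so the critical value is 0.0800. Power ≈ Φ((0.1015 − 0.0800) / (0.0408 × √(1 − ρ_S))). At ρ = 0.38 this is Φ(0.0215 / 0.0325) = Φ(0.66) = 0.745.

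**4. Simulation per branch** (10,000 replicates, bivariate normal, N=100, SD 22):

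| ρ | Rank-sum type I error | Rank-sum power | Signed-rank power |
|---|---|---|---|
| 0 | 4.9% | 0.71 | 0.70 |
| 0.2 | 3.0% | 0.72 | 0.79 |
| 0.38 | 1.3% | 0.75 | 0.89 |
| 0.5 | 0.6% | 0.77 | 0.94 |
| 0.6 | 0.2% | 0.79 | 0.98 |

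The formulas in steps 2 and 3 agree with the simulation to within about a point. At ρ = 0.4, rank-sum needs roughly 140 patients for 90% power, where signed-rank needs about 100.

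**5. The whole rule for adherence.** Assumptions: beta-shaped adherence, means 0.50 and 0.58, SD 0.22, 6,000 replicates. Anderson-Darling is applied at 0.05 to each time point, and a rejection at either leads to rank-sum. The rank-sum branch is then used in about 62–64% of trials.

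| ρ | Rule as written | Always paired t-test |
|---|---|---|
| 0 | 0.72 | 0.72 |
| 0.2 | 0.77 | 0.81 |
| 0.38 | 0.80 | 0.89 |
| 0.5 | 0.85 | 0.95 |

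With Anderson-Darling on the differences, the branch is used in about 4–7% of trials and the loss is about 1 point or less.

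**6. A skewed count (illustrative).** Assumptions: negative binomial, dispersion 1, mean 3 falling to 2, N=100. Anderson-Darling on the outcomes rejects in practically every trial. Rank-sum against signed-rank power is 0.56 against 0.62 at ρ = 0, 0.55 against 0.71 at 0.16, 0.57 against 0.82 at 0.34, and 0.57 against 0.90 at 0.49. Between 17% and 26% of pairs have a zero difference; these were dropped in the signed-rank test.

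**The case against.** The best defence is that this is a slip of the pen. Listing Wilcoxon and Mann-Whitney as separate options beside a paired t-test suggests that signed-rank was meant, and then no power is lost. That may be so, but the sentence is the operative rule for choosing the test, and it should name the right one.

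The loss may also be small. It vanishes at zero correlation. If outcomes are normal at each time, Anderson-Darling at 0.05 rejects at either time in at most about 10% of trials, so at ρ = 0.38 the cost is about 0.1 × 14 = 1.4 points. The larger losses for adherence need the literal reading of the normality check, a non-normal shape and positive correlation together. This stands as a limit on the size. The value 0.38 is likewise only one reading of Table X, and the count example has no source in the document.

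An independent-samples test could suit unlinked provider surveys or the comparison with historical rates in Specific Aim 1. But the sentence covers changes during the study and is not limited to those uses. Table 1 also marks no adherence value at Visit 1, so the pre score is undefined. That is a separate gap; it leaves the point intact for asthma control scores and other outcomes repeated on the same child.

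Finally, this is a pilot, and the error is conservative under positive correlation, so it does not create false claims of benefit. That limits the stakes, but a study that already calls itself underpowered should not give up power it could keep.

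**Conclusion.** The concern holds. As written, the non-parametric branch applies an independent-samples test to paired data, and no paired alternative is named. The defect can be read directly from the text and depends on no assumed figure.

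The size does depend on assumptions. For an 8-point change at N=100 with SD 22, the rank-sum branch costs nothing at correlation 0, about 14 points of power at 0.38 and about 17 at 0.5. Over the whole rule with beta-shaped adherence and the check on the outcomes, the cost is about 9 to 10 points at correlations of 0.38 to 0.5. It is about 1 point or less if the differences are checked. Skewed counts would be hit harder, because nearly every trial would take the rank-sum branch. Under positive correlation the type I error falls below 5%; only a negative correlation would inflate it (about 7.5% at −0.2). This should be fixed before analysis.

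**What to change.** Replace the two test-selection sentences in the Analysis plan with wording to this effect: *The Anderson-Darling test will be applied to the within-subject differences. Depending on the result, the paired t-test or the Wilcoxon signed-rank test will be used for change in any outcome measured repeatedly on the same patient or the same linked provider.*

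Also state:

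- how zero differences are handled for counts such as missed school days;
- whether provider pre and post surveys are linked, and which test applies if they are not;
- if an independent-samples test is wanted for the historical comparison, that it is kept for that purpose only.

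An option that avoids data-driven test choice for the primary outcome is to keep the paired t-test of the sample-size section as the primary adherence analysis, with signed-rank as a sensitivity analysis.

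The cost is two rewritten sentences and a few clarifications, with no added patients, data or expense.

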 - iii. Pediatric Inhaler Adherence Questionnaire, a self (or in the case of this study, phone administered) survey of barriers to medication adherence
 - iv. Parent attitudes towards medications and barriers to adherence.
 - v. Changes in adherence barriers and behaviors to improve adherence over time
 - vi. The number of asthma related readmissions or revisits between study visits will be self-reported.

- vii. The number of missed school days between visits will be self-reported.
- viii. Provider satisfaction will be recorded using the pre-post surveys

B. Description of Population to be Enrolled:

- a. Children admitted to Children’s Hospital Colorado inpatient or emergency department with a primary diagnosis of asthma exacerbation.
 - i. Inclusion criteria-patients
 - 1. Age 6-17 years
 - 2. On a controller medication at baseline
 - ii. Inclusion criteria-providers
 - 1. Aged 18-70
 - 2. Caring for a patient that is enrolled in the study
 - iii. Exclusion criteria
 - 1. Primary language other than English or Spanish (smartphone application only available in these languages)
 - 2. Homeschooled or not in school
 - 3. Significant developmental delay, cystic fibrosis, interstitial lung disease, tracheostomy/ventilator dependence
 - 4. Following up with a pulmonary or allergy provider outside of the CHCO system

C. Study Design and Research Methods

The proposed study is a single center trial at Children’s Hospital of Colorado, designed to evaluate the effects of a navigator program on medication adherence, provider communication and other asthma related health outcomes. Participants will be recruited from the population of patients between the age of 6 and 17 years admitted to Children’s Hospital Colorado inpatient or emergency department with a primary diagnosis of asthma exacerbation. Investigators plan on a one-year enrollment period and will follow each study participant for 3-6 months.

Recruitment

Upon admission hospital staff will identify potential participants based on the admission medical record. Patients will be approached by research staff and asked if they would like to participate in the study. A member of the research team (principally, the research coordinator) will do the recruiting. The research coordinator will explain the study and enroll subjects. Estimated duration is 45-60 minutes depending upon the patient.

Consent/Assent

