option to have access to their child's adherence information. The smartphone application also has portions dedicated to education about asthma triggers. Patients will be set up with a pulmonary or allergy follow up within 2-4 weeks of discharge. Patient's pulmonary or allergy providers will also be enrolled in the propeller health system, with access to the propeller health dashboard. Once providers receive access, they will be able to log-in and view all of their patients in list format. They will be able to see up to the minute data on patient adherence at any time that they choose to log-in to the dashboard. Providers will also receive email notifications if their patient has not used their controller medications for 7 days, or if their patient has had a significant increase in quick-relief medication use, indicating a worsening of asthma status (see figure 1 below). Patients will be monitored for a total of 3-6 months. The asthma navigator will contact the families at 2, 4 and 6 months post-enrollment, and discuss the patient's recorded adherence with the families. If a patient is enrolled for 4-5 months, we will discuss adherence at 2 and 4/5 months. If a patient is only enrolled for 3 months, we will discuss adherence at 2 and 3 months. Additionally, they will discuss any barriers to adherence that the family may be experiencing, and make referrals to social work as necessary, as well as attempt to brainstorm ways to improve adherence with the families. Additionally, the asthma navigator will collect each patients' adherence data and create an adherence report, which will be distributed on a monthly basis to the patient's primary care provider, pulmonary/allergy provider, and school nurse via email. The asthma navigator will be monitoring communications between the providers and marking the numbers of communications.

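### Readmissions and revisits have two unlinked sources, and emergency revisits rest on recall alone over follow-up that differs by child; the planned chart review should cover both

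*Combined protocol and SAP*

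**What the plan says.** Readmissions or revisits are one of the Aim 3 outcomes. Section IV.A, item c, lists "Other asthma related outcomes including asthma control test, symptom assessments, asthma related readmissions or revisits, missed school days, and provider satisfaction".

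Two rules then describe how such events are counted:

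- Section IV.A, item c.vi: "The number of asthma related readmissions or revisits between study visits will be self-reported".
- Section IV.F, Analysis plan: "Number of rehospitalizations will be obtained via chart review at 1 month, 6 months and 12 months post hospitalization".

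The self-report intervals follow the contact schedule in Section IV.C, Study Design: "The asthma navigator will contact the families at 2, 4 and 6 months post-enrollment". That schedule shortens for some children: "If a patient is only enrolled for 3 months, we will discuss adherence at 2 and 3 months". Overall, "Patients will be monitored for a total of 3-6 months".

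Section IV.B recruits children admitted to the "inpatient or emergency department with a primary diagnosis of asthma exacerbation", so some index encounters may be emergency visits only.

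Three other places bear on the point. The Analysis plan calls for a hospitalisation count, in a sentence about monthly summaries, and for per-child costs built from medical resource use; it names a source for neither. It also states that "asthma related health care use in the previous year will be obtained at enrollment". Section IV.D describes data collection as surveys and device data and does not list chart review.

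**The concern.** Rehospitalisation risk is the protocol's reason for choosing this population, so readers will look for this result even though it is not primary. As written, the figure for a given child depends on which rule the analyst follows. The rules differ in source, type of event, timing and length of observation. If the choice is left until the data are in, the hospitalisation summary and the cost totals can each be built from either count, and the more favourable one could be reported.

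Emergency revisits are the weaker part. The chart review, as worded, collects rehospitalisations only. Revisits therefore depend entirely on what a family remembers at a phone contact, over a period that is twice as long for some children as for others. The study has a single group, so no control arm would reveal an apparent change produced by the way events were counted.

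**Working it through.** The documents give no event rate, power or sample size for rehospitalisation, so there is no stated figure to reproduce. The check sets the two rules side by side and then compares their windows.

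**Side by side**

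| Element | Section IV.A, c.vi | Section IV.F, Analysis plan |
|---|---|---|
| Source | Family report | Chart review |
| Event | Asthma readmissions or revisits, together | Rehospitalisations; no cause stated, no revisits |
| Times | 2, 4 and 6 months; or 2 and 4/5; or 2 and 3 | 1, 6 and 12 months |
| Start | Enrolment | After hospitalisation |
| Length | 3 to 6 months, differing by child | Same for every child |

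The only shared time is month 6, and only for children followed for the full 6 months. No passage names one source as the analysed one, says how disagreements are settled, or says that one checks the other.

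**Window coverage** = months of self-report ÷ months of chart window

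| Self-report ends at | Share of 6-month window | Share of 12-month window |
|---|---|---|
| 3 months | 3/6 = 50% | 3/12 = 25% |
| 4 months | 4/6 = 67% | 4/12 = 33% |
| 5 months | 5/6 = 83% | 5/12 = 42% |
| 6 months | 6/6 = 100% | 6/12 = 50% |

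**What that does to the counts.** Assume a constant event rate, perfect recall, and the same events captured by both sources. The ratio of the 12-month chart count to the self-reported count is then 12/3 = 4 for a child followed 3 months and 12/6 = 2 for one followed 6 months.

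For 100 children, expected events = 100 × annual rate × months/12. The rates below are assumed, because the documents give none. The two ends of the self-report column are all children followed for 3 months and all followed for 6 months.

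| Assumed events per child-year | Self-report, 3 to 6 months | Chart, 6 months | Chart, 12 months |
|---|---|---|---|
| 0.2 | 5 to 10 | 10 | 20 |
| 0.4 | 10 to 20 | 20 | 40 |
| 0.6 | 15 to 30 | 30 | 60 |

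These figures show how far the answer moves with the choice of rule. They do not measure bias in either rule. The difference in event type (revisits in one, not the other; cause stated in one, not the other) comes on top and cannot be sized from the documents.

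**The case against.** The strongest reply is that the two rules are not in conflict. One is a short-term family-reported measure of readmissions and revisits; the other is a longer chart-based count of admissions. A study may have both. This stands: a reader might infer an outright contradiction over a single outcome, and the difference in event type argues against that. What is missing is the link between the measures and the analyses.

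Other parts of the reply also stand:

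- Chart review needs no visit, so chart times of 1 and 12 months are not a fault in themselves, nor is a chart window that outlasts monitoring.
- A reader might infer that children enrolled from the emergency department have no start date. The protocol speaks of admission for both routes and of discharge for enrolled patients generally, so the index encounter is an obvious origin. Whether a later first inpatient stay counts as a rehospitalisation is a wording question to settle.
- A reader might infer that follow-up will show a false fall against the previous year. That needs a source for previous-year use, which the plan does not give, and a comparison it does not specify: previous-year use is listed as baseline information, and tests concern changes during the study period.

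The reply also notes that a monthly hospitalisation count would adjust for unequal follow-up. That helps in part. It adjusts for length only if the rate is steady over time, and the plan still does not say which source would supply the count. Nothing in the reply gives emergency revisits a source other than recall.

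**Conclusion.** The point holds in a limited form. The plan has two differently defined counts and does not say which supplies the hospitalisation summary or the cost totals. Emergency revisits rest on recall alone, over 3 to 6 months depending on the child. Self-report spans 50% to 100% of the 6-month chart window and 25% to 50% of the 12-month window. These ratios follow directly from the stated schedules; the 2-to-4-fold difference in counts also assumes a constant rate and perfect recall.

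The documents support neither a numerical estimate of bias nor a claim that the two passages cannot both be carried out. The outcome is secondary, under Aim 3, in a study that calls itself an underpowered pilot, and the primary adherence analysis is unaffected. The change is worth making because it is cheap and replaces a recalled count of unequal length with a documented one of equal length.

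**What to change.** Rewrite Section IV.A, item c.vi, and the chart-review sentence in Section IV.F as one definition:

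1. Make the chart review already planned the source for every analysed count, including the hospitalisation summary. State that the utilisation part of the cost totals uses the same source.
2. Abstract dated, asthma-related admissions and emergency revisits as two separate counts, starting from the date of index discharge, whether inpatient or emergency department.
3. Do this at 1 and 6 months for every child, whatever the length of device monitoring. Keep the 12-month count, labelled as follow-up after navigator contact has ended.
4. Report family-reported events separately, over the period in which each child was contacted, for example to show events outside the hospital system. Do not merge them into the chart count: a child contacted for 3 months would have such events captured for only 3 of the 6 months, which brings unequal ascertainment back.
5. Describe previous-year use as a baseline characteristic only, and do not test it against follow-up.
6. List chart review among the data collection methods in Section IV.D.

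The cost is protocol wording and slightly more abstraction time. The remaining weakness is that charts may miss events treated elsewhere; the separate self-report summary shows some of these, but only for the contacted period.
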